## **2. Criteria for Subject Selection**

### **2.1 Number of Subjects**

A convenience sample of participants will be recruited via online advertising, social media, word of mouth, flyering, and recommendations by doctors, schools, and other youth and/or health-focused organizations. Limbix may also work with participant recruitment companies, such as TrialFacts and Dynata. Healthcare providers involved in identifying potential study participants may be compensated for recruitment efforts (based on hourly effort and not on number of referrals or enrolled participants). A total of 60 participants will be recruited in Phase I, and a minimum of 120 participants with PHQ-8  $\geq 10$  will be recruited in Phase II. A statistically powered Phase III study will be designed following completion of Phase II.

Preliminary power calculations revealed that a sample size of 175 will achieve 80% power to detect a moderate effect size (Cohen's  $d=0.5$ ) between Limbix Spark and active control at a significance level of 0.05 for a two-tailed t-test with an estimated 27% attrition rate. A moderate effect size is expected based on previous digital interventions with active controls for depression and evidence of superior efficacy for CBT-based interventions. An effect size will be calculated at the end of Phase II and may inform power calculations in determining sample size for Phase III.

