There will be two phases of this study. Phase I will evaluate feasibility of a minimum viable product (MVP) version of the Limbix Spark mobile app (Version 1) within the context of a real world deployment. After feasibility is established, Phase II will be initiated during which a primary outcome of effectiveness of the Limbix Spark app will be evaluated. At the commencement of Phase II, an updated version of Spark (Version 2) will be implemented. In order to quickly support teens during COVID-19 with an engaging and efficacious digital treatment, one additional app update is planned (Version 3) during Phase II. Recruitment for Phases I and II may not be powered to detect statistically significant differences between Spark and the educational control condition. Participants in Phase I will be randomized using a 1:1 ratio. Participants in Phase II will be randomized using a block randomization approach to ensure equal group sizes. Block size will range in multiples of 2 from 4-12 and be randomly generated to prevent guessing of allocation and eliminate bias.

In Phase I if the participant does not complete the post-intervention assessments within 4 weeks from the end of the intervention period they will be considered lost to follow up. If a participant chooses to withdraw from the study at any point or is deemed lost to follow up or dropped from the study during the intervention period (5 weeks), access to the web portal and mobile app will be restricted at that time. Otherwise, access to the mobile app will be restricted at the end of the 5-week intervention period and access to the web portal will be restricted after post-intervention assessments have been completed or the participant is deemed lost to follow up (4 weeks after intervention period). Participants will be compensated \$25 in the form of an electronic gift card or cash transfer for completing the post-intervention assessments regardless of adherence to their assigned intervention. Gift cards will be emailed to participants.

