## Phase II

The main purpose of Phase II is to evaluate the effectiveness of the Limbix Spark program relative to an educational control condition. All analyses will be restricted to those participants with PHQ-8  $\geq 10$  unless otherwise indicated. Data from participants who reported a change in their medication or treatment for a mental health disorder that occurred during the study may be excluded from primary analysis. The core analysis strategy in this project is longitudinal mixed effects modeling, where we fully utilize the repeatedly measured primary and secondary outcomes and maximum likelihood estimation will be applied.

Data across versions 2 and 3 will be pooled and statistical analyses conducted with the combined dataset may be computed with version included as a covariate. Statistical analyses may also be conducted separately for versions 2 and 3 cohorts. All analyses will be completed in line with the intent-to-treat (ITT) principle, where all participants will be included in the analyses according to their assigned study arm at baseline, regardless of adherence to study protocol. Modern per protocol analyses will also be conducted to estimate treatment effects for participants who adhered to the protocol. All analysis results will be two-tailed, with a significance level at 0.05 and 95% confidence intervals.

All measures will be analyzed using mixed effects modeling, followed by generalized estimating equations to account for irregularly spaced measurements, fully utilizing all repeated measures and all available data. Missing data will be imputed using multiple imputation and likelihood-based analyses. Case analysis or single

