Lastly, we will assess treatment adherence by evaluating treatment-related differences in rates of program completion and daily mobile app usage using independent samples (between treatment and control groups) or paired (within the educational control group) t-tests. We will also assess treatment-related differences in self-reported usability and engagement using the SUS and UES scales descriptively by comparing means and variability between groups and within group (control group only)

Statistical analyses for the primary outcome variable and between group differences in rates of clinical concerns rates will be conducted when N=60 (~30/grp) and N=120 (~60/grp) participants have completed Phase II. If no statistical differences are detected in the primary outcome variable, possible moderators of treatment status on the primary outcome may be evaluated, including age, concurrent treatment, and PHQ-8 score at baseline. Results of the interim analyses may be used to adjust recruitment targets for the remainder of the trial.

An effect size will be calculated for the primary outcome and may be used to determine sample size for a Phase III trial.

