This study may be stopped prior to its completion if: 1) study recruitment or retention is too low for the study to provide meaningful results; 2) new information becomes available during the trial that necessitates stopping the trial; 3) other situations occur that might warrant stopping the trial. Given that the trial intervention is relatively safe and updates to the mobile app are planned a priori, the trial will not be stopped prior to implementation of Spark version 3 for lack of demonstrated efficacy. The trial may be stopped early if PIs, in collaboration with study clinician and DSMB, determine from interim analyses during implementation of version 3 that the Spark app is not efficacious or if there are safety concerns. The trial will be stopped early if PIs, in collaboration with the study clinician, find that the harm to study participants outweighs the benefit of the scientific evidence to be accrued by continuing the trial at any time.

Unanticipated adverse device effects (UADE, as defined in 21 CFR 812.3, also referred to as "Unanticipated Problems"): Any serious adverse effect on health or safety or any life-threatening problem or death caused by, or associated with, a device, if that, effect, problem, or death was not previously identified in nature, severity, or

degree of incidence in the investigational plan or application; OR Any other unanticipated serious problem associated with a device that relates to the rights, safety, or welfare of subjects.

UADEs must meet all of the following criteria:

- Serious
- Associated with the device under investigation
- Unexpected
- Likely to require a significant change to study protocol (i.e., serious clinical concern occurring with a frequency or severity that changes such as modification of safety monitoring protocol or revision of inclusion/exclusion criteria would be required)

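### Phase II tests the primary outcome at 60 and 120 completers under an undivided 0.05, may change recruitment on the results, and names neither the decisive analysis nor an alpha rule

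*Combined protocol and SAP*

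**What the plan says.** - **Level.** Section 4.4, Phase II: "All analysis results will be two-tailed, with a significance level at 0.05 and 95% confidence intervals". No division across looks is given.
- **Looks.** The same section says that analyses of the primary outcome and of clinical concern rates "will be conducted when N=60 (~30/grp) and N=120 (~60/grp) participants have completed Phase II". Its next sentence depends on whether a statistical difference was found, so these are significance tests and not only descriptive looks.
- **Re-sizing.** "Results of the interim analyses may be used to adjust recruitment targets for the remainder of the trial". No rule is attached.
- **Sample size.** Section 2.1 recruits "a minimum of 120 participants with PHQ-8" of 10 or more in Phase II and states no maximum. A separate preliminary power statement there gives 175 for d=0.5 and 80% power, "with an estimated 27% attrition rate". It is not assigned to a phase.
- **Stopping.** Section 4.5 describes early stopping for lack of efficacy, for safety and for practical reasons, but not for success. It adds that "the trial will not be stopped prior to implementation of Spark version 3 for lack of demonstrated efficacy".
- **Status of Phase II.** Section 3.1: "Recruitment for Phases I and II may not be powered to detect statistically significant differences between Spark and the educational control condition". Section 2.1: "A statistically powered Phase III study will be designed following completion of Phase II". Section 4.4 nevertheless makes effectiveness the main purpose of Phase II.

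**The concern.** Testing the same outcome more than once at an unadjusted 0.05 raises the chance of a false positive if any of the tests can support a claim. Extending recruitment after seeing unblinded results can raise it too, even with a single test at the end. The plan allows both and does not say how the results will be used.

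The place of N=120 is also unclear. The looks are counted in completers and the Phase II target in recruits. On the plan's own attrition figure, the N=120 look could be the final analysis, an interim one, or never reached.

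Without a named decisive test, a reader cannot tell whether a Phase II p<0.05, or its 95% confidence interval, carries 5% error or more. The Phase II effect size may also set the size of Phase III.

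**Working it through.** **Inputs.** Two-sided 0.05, looks at 60 and 120 completers (section 4.4); minimum 120 recruited, d=0.5, 80% power, t-test, 27% attrition, N=175 (section 2.1); equal groups (section 3.1).

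**1. The plan's own figure.** Normal approximation: n per arm = 2(1.960 + 0.842)²/0.5² = 62.8, so 63; total 126; 126/0.73 = 172.6, so 173. Exact t-test: 63.77, so 64 per arm; 128/0.73 = 175.3 (174.7 from the unrounded n). The 175 reproduces.

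**2. Recruits against completers at 27% attrition.**
- 120 recruited: 120 × 0.73 = 87.6, about 88 completers.
- 120 completers: 120/0.73 = 164.4, about 165 recruited.
- 175 recruited: 175 × 0.73 = 127.75, about 128 completers.

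**3. Error with two looks.** Take information as proportional to the number analysed, so corr(Z₆₀, Z₁₂₀) = √(60/120) = 0.707. Under the null, P(|Z₆₀|>1.96 or |Z₁₂₀|>1.96) = 0.05 + 0.05 − P(both) = 0.10 − 0.0169 = **0.0831**. Simulated t-tests at 30 and 60 per arm (400,000 runs) give 8.4%. Treating the looks as independent would give 1 − 0.95² = 9.75%, which is too high because they share data.

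**4. Error by reading of the plan** (unadjusted two-sided 0.05 at each claim-bearing test):

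| Reading | Tests at N analysed | Type I error |
|---|---|---|
| One success test, fixed N | 120 | 5.0% |
| Claim at either look | 60, 120 | 8.3% |
| Recruitment ends at the stated minimum | 60, 88 | 7.6% |
| No claim at 60, further test after 120 | 120, 128 | 6.2% |
| same | 120, 175 | 7.6% |
| same | 120, 240 | 8.3% |
| Claim at any of three looks | 60, 120, 128 | 9.3% |
| same | 60, 120, 175 | 10.6% |
| same | 60, 120, 240 | 11.3% |

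The sizes 175 and 240 *analysed* are assumptions. No row is a ceiling, because the plan sets no maximum: a third test at 600 gives 12.3%. If the size of one further test were chosen from the N=120 data without limit, the worst case is 11.2% with no claim at N=60 and 14.1% with one.

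**5. Re-sizing alone.** Assume no claim at N=60, extension from 120 to 174 only when |t| at 120 lies between 1 and the critical value, and one unadjusted test at the end. The simulated error is about 7.4%. A single final test is therefore not enough if its N depends on unblinded results.

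**6. What would hold 5%.** Lan-DeMets O'Brien-Fleming-type spending applied to the total two-sided 0.05, α(t) = 2[1 − Φ(1.96/√t)]:
- Looks at 60 and 120: z = 2.772, 1.979; nominal p = 0.0056, 0.0478.
- Looks at 60, 120 and 128: z = 2.863, 2.041, 2.093; nominal p = 0.0042, 0.0413, 0.0364.

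Spending 0.025 on each side instead gives 0.0031, 0.0490 and 0.0021, 0.0405, 0.0389. Both conventions hold 5%.

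**7. Power at d=0.5** (normal approximation, Φ(0.5√(N/4) − 1.96)): N=120, Φ(0.779) = 78.2%; N=128, Φ(0.868) = 80.7%. With the boundaries for total two-sided 0.05: 77.8% for two looks and 79.6% for three. The t-test gives 77.5% and 80.1% for the fixed designs.

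**The case against.** The strongest reply is that no inflation has been shown. The plan nowhere permits stopping or claiming success at a look. The stopping it describes, for lack of efficacy or safety, cannot raise the type I error. The text speaks of interim analyses and of the rest of the trial, and the DSMB reviews interim results (section 4.5.2), so a natural reading is monitoring looks followed by one final test. **This stands in part.** It is why 5.0% is a legitimate reading and 8.3% is not the expected error. But a significant N=60 result can be reported while the trial continues, and nothing bars that. The DSMB text contains no boundary, and unblinded re-sizing can inflate even a single final test.

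Second, Phase II may be unpowered and a powered Phase III is planned. **This stands as a limit on severity.** It does not supply the rule. For Phase I, section 4.4 plays down formal testing; for Phase II it makes no such statement and prescribes 0.05 tests of effectiveness.

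Third, section 4.1 names the endpoint and section 4.4 the core model. **True**, but neither says which look decides.

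Fourth, completers are not the analysed set. The intention-to-treat mixed model also uses data from people who drop out, and for control participants it is unclear whether completing Phase II includes their later Spark period. **This stands for precision.** The one-half fraction for 60/120 is roughly robust to it. The 88 and 128 figures, and the boundaries built on 128, are approximate.

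**Conclusion.** The concern holds and should be fixed. The defect is a missing commitment, not a demonstrated error rate: the plan tests at two looks, allows re-sizing on the results, sets no maximum N, and names neither the decisive analysis nor an alpha rule. The error is 5.0% for one success test at a fixed N, and lower if a lack-of-efficacy stop is used. It is 8.3% if either planned look can support a claim, and 9.3% if a third test follows at 128 completers. These figures assume information proportional to the number analysed and an unadjusted two-sided 0.05 at each claim-bearing test. Confidence is high on the omission; the size depends on how the looks are used. The exploratory weight of Phase II limits the harm.

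**What to change.** Before the first unblinded look, adopt one of the following in section 4.4.

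**(a) One named test.** State that the N=60 look cannot support an efficacy claim. Name one final efficacy test at a fixed number of *analysed* participants, and re-size only on blinded variance or attrition. Any use of a look to judge lack of efficacy must be reconciled with section 4.5, which rules out such a stop before version 3; the plan does not say whether N=60 falls before or after that. *Cost:* SAP wording and giving up unblinded adjustment of recruitment. Power at N=120 and d=0.5 stays 78.2% with no lack-of-efficacy stop. For costing only, a stop at N=60 when the estimate favours control would give 77.9% and a type I error of 2.5%.

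**(b) Alpha spending.** Fix a maximum number analysed and apply a Lan-DeMets O'Brien-Fleming-type boundary over every look including the last, stating the spending convention. If unblinded results may change N, use an inverse-normal combination with pre-fixed weights; with weights 60/60/8 and the three-look boundary, the simulated error is 5.00%. *Cost:* power at d=0.5 falls from 78.2% to 77.8% with two looks ending at 120, and from 80.7% to 79.6% with looks at 60, 120 and 128.

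Under either option, say whether N=60 and N=120 count recruits, completers or analysed participants, and define completion of Phase II for the control arm.

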#### **4.5 Data Monitoring**

This is a low risk research study.

A clinical concern is defined here as any negative experience or symptom reported by participant or parent in the Participant Symptom Check Questionnaire, in freeform text, spontaneously reported, or clinically significant deterioration of symptoms, whether or not thought to be associated with participation in the study.

Clinical concerns will be categorized as follows:

0- Not a clinical concern: Research team determined that triggering event was not a clinical concern

1- Mild clinical concern: Research team determined that triggering event doesn't require clinician input and will continue to monitor participant's responses

2- Moderate clinical concern: Research team determined that triggering event requires clinician input. Clinician determined that research team should continue to monitor participant's responses but that no follow-up was needed.

3- Elevated clinical concern: Research team determined that triggering event requires clinician input. Clinician determined follow-up was indicated and confirmed participant safety (participant did not endorse intent to self harm) via email or phone communication with participant or their parent/guardian or their provider.

4- Significant clinical concern: Research team determined that triggering event requires clinician input. Clinician determined that follow-up was indicated and after follow-up with participant, parent/guardian, or provider determined that participant should be withdrawn from study (e.g. due to suicide attempt, self-harm or self-harm attempt, suicidal ideation with intent, reported hospitalization for self-harm or suicide attempt while enrolled in study).

All adverse device effects and complaints will be recorded (whether anticipated or unanticipated). The project PI and study clinician will determine whether it is in the participant's best interest to remain in the study after any clinical concern.

Anticipated serious clinical concerns, given the study population, include depressive symptoms as defined in the DSM-V, suicidal ideation, active self-harm, clinically significant deterioration in depressive symptoms, suicide attempts, and suicide.

This study may be stopped prior to its completion if: 1) study recruitment or retention is too low for the study to provide meaningful results; 2) new information becomes available during the trial that necessitates stopping the trial; 3) other situations occur that might warrant stopping the trial. Given that the trial intervention is relatively safe and updates to the mobile app are planned a priori, the trial will not be stopped prior to implementation of Spark version 3 for lack of demonstrated efficacy. The trial may be stopped early if PIs, in collaboration with study clinician and DSMB, determine from interim analyses during implementation of version 3 that the Spark app is not efficacious or if there are safety concerns. The trial will be stopped early if PIs, in collaboration with the study clinician, find that the harm to study participants outweighs the benefit of the scientific evidence to be accrued by continuing the trial at any time.

Unanticipated adverse device effects (UADE, as defined in 21 CFR 812.3, also referred to as "Unanticipated Problems"): Any serious adverse effect on health or safety or any life-threatening problem or death caused by, or associated with, a device, if that, effect, problem, or death was not previously identified in nature, severity, or

degree of incidence in the investigational plan or application; OR Any other unanticipated serious problem associated with a device that relates to the rights, safety, or welfare of subjects.

UADEs must meet all of the following criteria:

- Serious
- Associated with the device under investigation
- Unexpected
- Likely to require a significant change to study protocol (i.e., serious clinical concern occurring with a frequency or severity that changes such as modification of safety monitoring protocol or revision of inclusion/exclusion criteria would be required)

PIs will report unanticipated adverse device effects to the IRB and DSMB within 10 working days. Limbix will immediately conduct an evaluation of any reported unanticipated adverse device effect and will report such effects to the FDA within 10 working days. If it is determined that an unanticipated adverse device effect presents an unreasonable risk to subjects, the investigation or parts of the investigation presenting that risk will be terminated as soon as possible. Termination shall occur not later than 5 working days after the sponsor makes this determination and not later than 15 working days after the sponsor first received notice of the effect. Limbix will not resume a terminated investigation without IRB approval and, if the investigation was terminated under paragraph (b)(2) of 21 CFR 812.46, FDA approval.

Limbix will submit to FDA a copy of any report by an investigator under paragraph (a)(5) of section 21 CFR 812.150 of use of a device without obtaining informed consent, within 5 working days of receipt of notice of such use.

Per 21 CFR 56.108(b)(1) and 21 CFR 812.150(a)(1), PIs will report any unanticipated problem involving risk to human subjects or others to the IRB.

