## Schedule of Assessments:

|  | Baseline | Weekly during study | Post-intervention |
|--|----------|---------------------|-------------------|
| Patient Health Questionnaire (PHQ-8)                   | X        | X                   | X                 |
| Baseline Questionnaire- Participant                    | X        |                     |                   |
| Baseline Questionnaire- Parent                         | X        |                     |                   |
| Brief Resilience Scale                                 | X        |                     |                   |
| Generalized Anxiety Disorder (GAD-7)                   | X        |                     | X                 |
| PROMIS Pediatric Global Health Scale                   | X        |                     | X                 |
| PROMIS Parent Proxy Global Health Scale                | X        |                     | X                 |
| Mood and Feelings Questionnaire (Short Parent Version) | X        |                     | X                 |
| Participant Symptom Check- Participant                 |          | X                   |                   |
| Participant Symptom Check- Parent                      |          | X                   |                   |
| Post Program Questionnaire- Participant                |          |                     | X                 |
| Post Program Questionnaire- Parent                     |          |                     | X                 |
| System Usability Scale                                 |          |                     | X                 |
| User Engagement Scale                                  |          |                     | X                 |

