###### Phase II

- Remission rates based on PHQ-8 < 10
- Between-group treatment-related differences in participant-rated anxiety symptoms and global functioning as measured by GAD-7 and PROMIS Pediatric Global Health Scale
- Between-group treatment-related differences in parent-reported depressive symptoms and global functioning as measured by MFQ, and PROMIS Parent Proxy Global Health Scale
- Average treatment-related usability (SUS) and engagement (UES-SF) ratings
- Between-group treatment-related differences in clinical concern rates and serious clinical concerns
- Between-group treatment-related differences in program adherence and engagement based on behavioral and mobile app analytics
- 

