imputation methods may also be used and a specific approach for imputation will be selected based on key attributes of the obtained data, including % missing and whether data are missing at random^109. Sensitivity analyses will be conducted to determine if data are missing at random. In these analyses, allowing for random intercepts and slopes, the change (slope) will be the key dependent variable and the randomization status will be the key independent variable. The results of these analyses can be easily converted to group or treatment differences at post assessments. In our mixed effects modeling, all variables will be analyzed as continuous with the exception of clinical concerns (occurrence/non-occurrence), which will be treated as a repeatedly measured binary outcome.

As an exploratory investigation, multiple variables will be investigated as possible moderators of treatment effects on depressive symptoms (PHQ-8). For example, we may evaluate medication status, symptom severity, age, sex, COVID19 specific factors, and aspects of program engagement (e.g., time to complete program, duration of use) as potential moderators. For this investigation, we will employ the MacArthur framework for moderator analysis, following the eligibility and analytical criteria for determining moderators. To maximize power, moderator analyses will also be conducted using mixed effects modeling.

Exploratory analyses using mixed effects modeling will also be conducted to evaluate whether successive program updates (between versions 2 and 3 of Limbix Spark) result in statistically significant differences on primary and secondary outcome measures, including depressive symptoms, global functioning, and treatment adherence, usability, and engagement.

Content analysis of post-study interviews will be conducted. Data will be codified to identify themes with an emphasis on engagement, usability, comprehension, therapeutic alliance, and overall impact of treatment. Key insights will be drawn from themes and contextualized with quantitative user session data.

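### Clinical-concern rates mix symptoms present at entry with new ones, because the symptom check has no baseline reading and a concern need not be new or worse

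*Combined protocol and SAP*

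**What the plan says.** Section 4.5 defines a clinical concern to include "any negative experience or symptom reported by participant or parent in the Participant Symptom Check Questionnaire", "whether or not thought to be associated with participation in the study". Free text, spontaneous reports and clinically significant deterioration also count. Only the deterioration item implies a change from an earlier state.

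In the Schedule of Assessments, the row "Participant Symptom Check- Participant" and the matching parent row are marked under the weekly column only. Section 3.4 describes the check as covering the concern, its severity and its relationship to the intervention. It does not mention onset or prior status.

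Section 2.5 requires self-reported depressive symptoms for Phase II, and section 4.4 restricts the Phase II analyses to PHQ-8 of 10 or more unless otherwise indicated.

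Section 4.2 lists as a Phase II secondary outcome "Between-group treatment-related differences in clinical concern rates and serious clinical concerns". Section 4.4 models "clinical concerns (occurrence/non-occurrence), which will be treated as a repeatedly measured binary outcome", and compares concern rates between arms when 60 and then 120 participants have completed Phase II.

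On seriousness, section 4.5 says: "Anticipated serious clinical concerns, given the study population, include depressive symptoms as defined in the DSM-V". Clinically significant deterioration is a separate item in that list. The 0–4 grading in the same section does not use the word serious.

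**The concern.** A participant who enrols with low mood and reports the same low mood at week 1 meets the section 4.5 definition of a concern. The symptom check holds no earlier reading that would show the report to be unchanged. Such reports add a background of events that neither app caused.

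In an occurrence/non-occurrence outcome, that background uses up room: someone already counted for an entry symptom cannot be counted again for a new one in the same period. The measured difference between arms is then smaller than the difference in new concerns.

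At stake is how well the Phase II safety comparison, including its two interim looks, can detect concerns that arise on treatment. The serious category has a related problem. The only description of it names depressive symptoms as such, which the analysed population has at entry.

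**Working it through.** **The plan's own figure.** The documents give no expected rate, power or sample size for clinical concerns. The one sample size, 175 in section 2.1, is for the PHQ-8 comparison. It reproduces (63.77 per arm by two-sample t-test; 2 × 63.77 / 0.73 = 174.7) and does not bear on this point.

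**Inputs**
- From section 4.4: about 60 per arm at N=120 and about 30 per arm at N=60; two-sided 0.05.
- Assumed: new-concern rates of 10% v 30%, with 5% v 20% as a second case.
- Assumed: a share b of participants who report an entry symptom at least once and have it counted. It is taken as equal in both arms and independent of new concerns.

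**Dilution.** With new-concern rate e, the observed rate is p = b + (1 − b)e. The observed difference is therefore (1 − b)(e_T − e_C), the true difference multiplied by (1 − b).

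**Power.** Φ[(d − 1.96·SE0)/SE1], where d is the observed difference, SE0 = √(2p̄(1 − p̄)/n) and SE1 = √([p_C(1 − p_C) + p_T(1 − p_T)]/n).

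At b = 0 and n = 60: SE0 = √(2 × 0.20 × 0.80/60) = 0.0730 and SE1 = √((0.09 + 0.21)/60) = 0.0707. Power is Φ[(0.20 − 0.1431)/0.0707] = 0.79.

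At b = 0.3: p_C = 0.3 + 0.7 × 0.10 = 0.37 and p_T = 0.3 + 0.7 × 0.30 = 0.51. SE0 = 0.0906 and SE1 = 0.0897. Power is Φ[(0.14 − 0.1776)/0.0897] = 0.34.

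| b | Observed rates | Difference (points) | Power, 60 per arm |
|---|---|---|---|
| 0 | 10% v 30% | 20 | 0.79 |
| 0.3 | 37% v 51% | 14 | 0.34 |
| 0.5 | 55% v 65% | 10 | 0.20 |
| 0.7 | 73% v 79% | 6 | 0.12 |

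For 5% v 20% the pattern is the same. Power is 0.70 at b = 0, 0.30 at b = 0.2 (24% v 36%) and 0.10 at b = 0.6 (62% v 68%).

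At 30 per arm with no background, power is only 0.49 (10% v 30%) or 0.42 (5% v 20%). The first interim look is weak even with clean counting.

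**Which events are affected.**
- Depressive deterioration can be referenced to the in-app PHQ-8 that section 3.1 makes compulsory at baseline.
- Lifetime suicide attempt, active self-harm and active ideation with intent are exclusions in section 2.6, so later occurrences are new on study.
- Other symptom-check items have neither protection. Suicidal ideation appears on the serious list without the intent qualifier, so ideation without intent could pre-date entry.

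**The case against.** Several counter-arguments have weight.

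1. **Existing references to baseline.** A reader might infer that no treatment-emergent rate can be derived. The documents do not support that, given the compulsory baseline PHQ-8 and the entry exclusions. The gap is confined to other symptom-check reports. The baseline questionnaire in section 3.4 takes clinical history but is not described as covering the symptom-check items.

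2. **Grade 0.** The research team can rule that a trigger is not a concern, which could remove unchanged entry symptoms. This stands as a possible mitigation. However, section 4.5 gives no criterion for the ruling and no baseline check to apply it against, and section 4.4 does not say how a grade 0 trigger enters the model.

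3. **The planned model.** Section 4.4 plans a repeated binary outcome, not an ever-occurrence test. A single week 1 report marks that week only, and persistent reporting is partly absorbed by participant effects. The power figures above are therefore not those of the planned analysis. The loss does not disappear, because a week already scored for an old symptom cannot register a new one.

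4. **Unknown instrument and rates.** The form's questions and recall period are not in the documents, so how often unchanged symptoms would be reported is unknown. A reader might infer that a real safety difference is certain to be hidden; that is not established.

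5. **The serious list.** It is worded as what is anticipated. A reader might infer that every participant's entry depression will be scored as serious, but the list is not written as an endpoint rule. What stands is that no other description of the category is given.

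6. **Other safeguards.** Randomisation balances the background, and under section 4.5.2 the DSMB reviews all concerns quarterly. So this is a loss of sensitivity in one comparison. It neither biases that comparison towards one arm nor leaves safety unmonitored.

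**Conclusion.** The point holds in this form. As defined, concern rates drawn from the symptom check combine entry symptoms with new ones, and the check has no baseline reading to separate them. The arm comparison is not biased by this, but its difference is pulled towards zero by about (1 − b). That factor assumes equal background in both arms and independence of old and new reports.

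The actual size is unknown: it depends on reporting rates that the documents do not state and on how grade 0 is applied. The fall from 0.79 to 0.34, 0.20 and 0.12 illustrates the mechanism under assumed rates and a simple ever-occurrence test; it is not a forecast for the planned model. The change is worth making because it is cheap and improves a secondary outcome that is also compared at both interim looks.

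**What to change.** - **Baseline reading.** Add the symptom and severity items of the Participant Symptom Check, participant and parent versions, to the existing baseline portal session, before app access. Omit the relationship-to-intervention item, which cannot be answered before exposure.
- **Comparison.** In sections 4.2 and 4.4, count only concerns that are new or worse than baseline for the between-arm comparison, including the interim looks. Keep the all-reports rate as a supporting analysis, and state how grade 0 triggers are counted.
- **Serious.** For that comparison, do not count unchanged entry-level depressive symptoms as serious, and reconcile the section 4.5 list with the 0–4 grading. The grades describe how staff handled an event, so a grade cut-off alone may not be a suitable definition of seriousness.
- **Unchanged.** Safety monitoring and follow-up of every report stay as they are.

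The cost is a few minutes at baseline, a portal copy of the participant items (which are otherwise delivered in the app) and some protocol wording.
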